7.2 Sample Size Calculation & Power Analysis

Statistical power and sample size are based on previous studies investigating differences in plasma amino acids in younger and older adults following the ingestion of 10 grams of free form essential amino acids (12). For peak EAA concentrations previous studies have demonstrated an effect size (Cohen's D) of 1.6 between health young and individuals with incipient sarcopenia. This effect size indicates we need 8 individuals in each group to detect a significant difference at an alpha level of 0.05 with 80% power.

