2.0 Hypotheses

We hypothesize that plasma amino acid response will be altered in elderly sarcopenic adults as compared to young and elderly healthy subjects.

We also hypothesize that the pharmacokinetics of plasma amino acids can be used to distinguish sarcopenic elderly from young and elderly healthy.

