3.0 Study Design and Procedures

We will enroll up to 35 subjects with a goal to study up to 30 healthy male and females: a group of 10 whose age is between 18 and 30 years, a group of 10 whose age is 70-89 years without the presence of sarcopenia, and a group of 10 whose age is 70-89 years with sarcopenia. We will use a 5-hour (one hour prior and 4 hours post-consumption of an amino acid supplement) period to completely characterize the plasma amino acid response to 10 grams of free-form essential amino acids of which 10% of the leucine content has been enriched with L-[1-13C] leucine. The principal end-point will be plasma amino acid response over the 4 hours following the consumption of the study product.

Secondary endpoints include body composition and total body water measurements. Small shifts in fluid from the extracellular to intracellular space likely correspond with EAA appearance and disappearance in plasma. BIA is a non-invasive, rapid assessment that is sensitive to acute shifts in fluid that are associated with disease and malnutrition states, such

Version #: 10 IRB# 262590 Page 7

Date: 31May22

Institution: UAMS

Sponsor: UAMS/TRI

as sarcopenia. As an exploratory analysis, we will measure acute shifts in total body,

intracellular, and extracellular fluid using multifrequency BIA throughout visit 2. This will serve

as preliminary data on a potential non-invasive method to evaluate muscle quality, anabolic

resistance, and a proxy indicator of sarcopenia.

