4.0 Study Population

Up to 35 subjects will be enrolled in order to meet the goal of 10 completers in each of the three groups. Attempts will be made to balance sexes within groups.

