7.0 Data Analysis

7.1 Statistical Analysis plan

Means by which experimental data will be analyzed or interpreted: Changes in the plasma amino acids area under the curve (AUC), maximal amino acid concentration, change from basal to maximal amino acid concentrations, rate to maximal amino acid concentration, and the clearance rate of amino acids from the plasma will be assessed with an one-way ANOVA with appropriate post hoc testing. Statistical significance will be accepted at an alpha level of p ≤ 0.05 .

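### Does section 7.2 need new power figures because its calculation covers only healthy young versus incipient sarcopenia?

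*Combined protocol and SAP*

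**What the plan says.** Section 7.2 gives one power statement. It draws on earlier work in younger and older adults given 10 g of free-form EAA: "For peak EAA concentrations previous studies have demonstrated an effect size" (Cohen's d) "of 1.6 between health young and individuals with incipient sarcopenia". It concludes: "This effect size indicates we need 8 individuals in each group to detect a significant difference at an alpha level of 0.05 with 80% power". It names no test, sidedness or adjustment.

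Section 7.1 lists five plasma measures, peak concentration among them, which "will be assessed with an one-way ANOVA with appropriate post hoc testing", at a 0.05 significance level. The post hoc method is not named.

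Section 2.0 states two hypotheses. The first is that "plasma amino acid response will be altered in elderly sarcopenic adults as compared to young and elderly healthy subjects". The second is that amino acid pharmacokinetics "can be used to distinguish sarcopenic elderly from young and elderly healthy". Both set the sarcopenic group against two comparators.

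Section 3.0 describes three groups of 10, including "a group of 10 whose age is 70-89 years without the presence of sarcopenia". Section 4.0 allows enrolment of up to 35 "in order to meet the goal of 10 completers in each of the three groups".

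**The concern.** There appear to be two mismatches.

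First, 8 per group is the answer for a single unadjusted two-group comparison, whereas 7.1 plans three groups with post hoc testing. An adjustment for three pairs costs power, so 8 per group could fall below the stated 80%.

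Second, the effect size compares healthy young people with people who have incipient sarcopenia, so it mixes the effect of age with that of sarcopenia. The comparison that separates the two is sarcopenic versus non-sarcopenic elderly, both aged 70 to 89. Both hypotheses include it, yet the plan gives it no effect size, power or detectable difference. A reader who took the 80% to cover every comparison could read a non-significant elderly result as stronger evidence of no difference than 10 per group can supply.

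**Working it through.** **Inputs.** d = 1.6, alpha = 0.05, target power 80% and 8 per group (section 7.2); three groups (sections 3.0 and 7.1); 10 completers per group (sections 3.0 and 4.0). Assumptions: two-sided tests, normal outcomes, common SD.

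**Step 1. Reproduce the plan's figure.** For a two-sample t test with n per group, the noncentrality is d × √(n/2) with 2n − 2 degrees of freedom.

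- n = 7: 1.6 × √3.5 = 2.993, df 12, critical value 2.179, power 78.5%.
- n = 8: 1.6 × √4 = 3.200, df 14, critical value 2.145, power 84.5%.

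Eight is the smallest size that reaches 80%, exactly as stated. The match suggests an unadjusted two-sided t test, but this is an inference because 7.2 names no test.

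**Step 2. The same comparison inside the three-group analysis.** The noncentrality is unchanged (3.200 at n = 8, 3.394 at n = 9, 3.578 at n = 10). The error is pooled over three groups, with 3n − 3 degrees of freedom. The Tukey critical value is q(0.95; 3, df)/√2. Bonferroni over three pairs uses alpha 0.05/3. F-protected LSD requires a significant overall F and then an unadjusted pairwise test. It was simulated (400,000 replicates) with the third mean equal to either of the other two or midway between them, hence the range.

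| Method | n = 8 | n = 9 | n = 10 |
|---|---|---|---|
| Bonferroni, 3 pairs | 72.1% | 78.7% | 83.9% |
| Tukey | 74.6% | 80.8% | 85.6% |
| F-protected LSD | 76–82% | not run | 86–91% |

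At 8 per group, whether power reaches 80% depends on the method and, for LSD, on where the third mean lies. At the planned 10, every method exceeds 80%.

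**Step 3. Sarcopenic versus non-sarcopenic elderly.** With no effect size in the documents, the useful quantity is the difference detectable with 80% power at n = 10 (pooled error, df 27). The 95% interval half-width is the critical value × √(2/10), that is, × 0.447.

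| Method | Critical value | Difference with 80% power | Interval half-width |
|---|---|---|---|
| Unadjusted | 2.052 | 1.30 SD | 0.92 SD |
| Bonferroni, 2 contrasts against the sarcopenic group | 2.373 | 1.45 SD | 1.06 SD |
| Tukey | 2.479 | 1.50 SD | 1.11 SD |
| Bonferroni, 3 pairs | 2.552 | 1.53 SD | 1.14 SD |

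These follow from n alone and do not depend on the young group's mean.

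**Step 4. What new text would change.** The group sizes would stay at 10. The pairwise comparisons are already provided for by the post hoc testing in 7.1. The intervals in step 3 can be computed at analysis whether or not 7.2 foresees them.

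**The case for a change.** The strongest case for a change is that the omitted comparison is the one that matters most. Discriminating elderly from young does not establish a test for sarcopenia; discriminating sarcopenic from healthy elderly would. The sponsor chose to give a power calculation, describes only the bioimpedance measure as preliminary, and tests at 0.05, so the calculation might be expected to cover the hypotheses or to say that it does not. A detectable difference needs no earlier elderly data, and adding it costs one sentence.

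Much of this stands. The omission is real, d = 1.6 cannot be carried over to the elderly comparison, and an interval of about ±0.9 to ±1.1 SD is wide. Two things weaken the case. Section 7.2 names its comparison openly, so a careful reader will not take the 80% to cover the others. Section 1.2 describes separating elderly from young as a first step towards a diagnostic test, which is close to the comparison that was powered, although section 2.0 goes further.

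Any sentence with figures would also have to be conditional, because the number depends on a post hoc method that 7.1 leaves open. Fixing Tukey figures in 7.2 while the method is undecided would create a new inconsistency.

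**Conclusion.** No change is needed. The stated 8 per group is right for the comparison that 7.2 names, and the planned 10 completers per group give 84% to 91% power for it under the three usual post hoc methods examined. The shortfall at 8 under Tukey (74.6%) or Bonferroni (72.1%) has no consequence if the planned 10 are reached.

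For sarcopenic versus non-sarcopenic elderly, power is unstated. That does not show it to be inadequate: 10 per group gives 80% power for about 1.3 SD unadjusted or 1.5 SD with Tukey or three-pair Bonferroni, and the documents give no basis for saying that the true difference is smaller. Disclosing this in 7.2 would be optional. It would alter no subject, test or conclusion, provided that a non-significant elderly result is read against its interval and not taken as proof of no difference.

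These figures assume two-sided testing, normal outcomes with a common SD, and 10 completers in each group. They apply to one measure at a time, with no adjustment across the five measures in 7.1. The 84% to 91% also rests on the d = 1.6 given for peak EAA, whereas section 3.0 names the plasma response over 4 hours as the principal endpoint; the documents give no effect size for any other measure.

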7.3 Sample Processing and Analyses

Blood samples will be processed and analyzed as described by PI's lab (2). Blood samples will be analyzed via LCMS to determine the concentration of specific amino acids relevant to the hypothesis. If performed, glucose and insulin concentrations will be performed using a COBAS analyzer. Stable isotope concentrations will be measured using either GC-MS or LCMS methods, if performed. Breath samples will be analyzed in real time via the collection apparatus. After all data has been analyzed and verified, samples will be discarded into a biohazard trash bag and disposed in accordance with UAMS biohazardous waste policy.

7.4 Grouping

Subjects in the older groups will be divided into either sarcopenic or non-sarcopenic based on the results of the handgrip assessment at visit 1 and amount of lean tissue derived from the

body composition measurements. The thresholds (per the Sarcopenic Definitions and Outcomes Consortium) are as follows:

Men whose value is < 35.5 kg are considered to have low muscle strength. Women whose value is < 20 kg are considered to have low muscle strength.

8.0 Ethical Considerations

This study will be conducted in accordance with all applicable government regulations and University of Arkansas for Medical Sciences research policies and procedures. This protocol and any amendments will be submitted and approved by the UAMS Institutional Review Board (IRB) to conduct the study.

The formal consent of each subject, using the IRB-approved consent form, will be obtained before that subject is submitted to any study procedure. All subjects for this study will be provided a consent form describing this study and providing sufficient information in language suitable for subjects to make an informed decision about their participation in this study. The person obtaining consent will thoroughly explain each element of the document and outline the risks and benefits, alternate treatment(s), and requirements of the study. The consent process will take place in a quiet and private room, and subjects may take as much time as needed to make a decision about their participation. Participation privacy will be maintained and questions regarding participation will be answered. No coercion or undue influence will be used in the consent process. This consent form must be signed by the subject and the individual obtaining the consent. A copy of the signed consent will be offered to the participant, and the informed consent process will be documented in each subject's research record.

9.0 Dissemination of Data

Results of this study may be used for presentations, posters, or publications. The publications will not contain any identifiable information that could be linked to a participant.

